1.1 HYPOTHESIS

The purpose of this study is to determine if performed force measurements yield a different recommended weight lifted during the sternotomy healing process than the traditional gold standard of 5 pounds. A secondary endpoint data obtained will be scores from the pre and post-activity questionnaires.

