1.2 STATISTICAL METHODOLOGY

Continuous variables will be reported as means and standard deviations or medians and interquartile ranges, if skewed. Categorical variables will be reported as frequencies and per cents. To do so, patients will use the PRIMUS equipment to obtain the maximum force pounds performed during six activities. Then, their new recommended weight to lift will be 30% and 50% of that maximum. We will use a one sample t-test to determine if a difference exists between the gold standard recommendation and the force performed in the activities.

With a sample size of 130 subjects, we will have in excess of 90% power to detect a difference of 5 pounds from the gold standard recommendation, assuming a standard deviation of 5 and a type I error rate of 0.05 in a two-tailed test. With this sample size, the data will likely be normally distributed, which is a necessary assumption to perform the one sample t-test. However, if the data do not meet this assumption, we will proceed using a nonparametric alternative, the Wilcoxon Rank Sum Test.

Additionally, to examine the change in confidence after performing the 6 activities, 2 surveys will be administered: 1 prior to treatment and 1 after treatment. In the survey, subjects will be asked to rate their confidence using a 7-point Likert scale to perform selected daily tasks. Subjects' perceptions of confidence will be reported and analyzed in several ways. We will consider the changes from each of the 7 categories, the change in

percent of ‘top box’ responses, and the changes in stratified responses (positive, neutral, negative).

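### Replacing the one-sample t-test with a rank test when forces are not normal does not hold the 0.05 level under right skew; at n=130 the t-test of the mean needs no such switch

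*Combined protocol and SAP*

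**What the plan says.** Section 1.1 sets the comparison: whether measured forces lead to a recommended weight other "than the traditional gold standard of 5 pounds". Section 1.2 names the test: "We will use a one sample t-test to determine if a difference exists between the gold standard recommendation and the force performed in the activities". The power statement opens "With a sample size of 130 subjects, we will have in excess of 90% power". The effect it has in view is a 5 lb departure from the standard, and its other inputs are given as "assuming a standard deviation of 5 and a type I error rate of 0.05 in a two-tailed test".

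The reason given for the t-test is "With this sample size, the data will likely be normally distributed, which is a necessary assumption to perform the one sample t-test". The fallback follows directly: "However, if the data do not meet this assumption, we will proceed using a nonparametric alternative", which the plan names as the Wilcoxon rank sum test. The same section expects that some continuous variables may be skewed, since it will report "means and standard deviations or medians and interquartile ranges, if skewed".

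The plan does not state how normality will be judged, whether the null concerns a mean or a median, any symmetry condition for the rank test, or the expected shape of the force distribution.

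**The concern.** The rule rests on two premises that do not hold. A larger sample does not make the data more normal; it makes the sample mean more nearly normal. That is all the t-test needs, and 130 patients supply it under ordinary skew.

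The replacement is more fragile than the test it replaces. A one-sample signed-rank test is a test of a mean or median of 5 lb only if the distribution is symmetric. Skew is a common reason for abandoning a t-test, and it is exactly what breaks the signed-rank test. The rule would then change the question after the data have been seen. It could declare a departure from 5 lb when the mean is 5 lb, or miss a mean modestly above 5 lb.

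**Working it through.** **Inputs from the plan (Sections 1.1 and 1.2).** n = 130, one group; null value 5 lb; difference 5 lb; SD 5 lb; two-sided alpha 0.05.

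**Assumptions, not in the plan.** Force shapes (gamma and lognormal, CV 0.2 to 1.0, plus symmetric shapes); Shapiro-Wilk at 0.05 as the normality check; signed-rank as the one-sample rank test intended.

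**1. The plan's power figure.** Noncentrality = (5/5) × √130 = 11.4 on 129 df. Power exceeds 99.99%, which agrees with the statement of more than 90%. Thirteen subjects would already give 90%.

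**2. Why skew breaks the signed-rank test.** The statistic W is the sum of the ranks of |x − 5| over patients with x > 5. Under symmetry about 5:

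- mean of W = n(n+1)/4 = 130 × 131/4 = 4257.5
- variance of W = n(n+1)(2n+1)/24 = 130 × 131 × 261/24 = 185,201, so SD = 430

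Under right skew with mean 5, W is no longer centred there:

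| Force distribution, mean 5 lb | P(force > 5) | Median | Pseudo-median | Average z of signed-rank |
|---|---|---|---|---|
| Gamma, skewness 1 (SD 2.5) | 0.433 | 4.59 | 4.79 | −0.92 |
| Exponential, skewness 2 (SD 5) | 0.368 | 3.47 | 4.20 | −1.89 |

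The signed-rank test is in effect testing whether the pseudo-median is 5, and here it is not. In the exponential case z averages close to the critical value of −1.96, so nearly half of trials reject.

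**3. False-positive rate with true mean exactly 5 lb, n = 130 (simulation).**

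| CV | Two-stage rule (gamma to lognormal) |
|---|---|
| 0.2 | about 6-9% |
| 0.4 | 11-21% |
| 0.6 | 20-38% |
| 1.0 | 46-72% |

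The t-test alone rejects about 4.5-6.7% across these settings; the top value is for the lognormal with CV 1.0 (skewness 4). Shapiro-Wilk triggers the switch in about a third of samples at gamma CV 0.2, and in 90-100% at CV 0.4 or more. At CV 0.4 or more, nearly all false rejections point below 5 lb. Simulation error is small: for a rate of 20% from 3,000 trials, √(0.2 × 0.8/3000) = 0.7 percentage points.

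**4. Symmetric non-normal data.** For uniform, Laplace and t (3 df) forces, signed-rank rejects 4.9-5.1%. The inflation comes from skew, not from non-normality as such.

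**5. Power.** At the planned alternative (mean 5 + 5 = 10 lb, SD 5) both tests reject essentially 100% of the time. At mean 6 lb with gamma CV 0.6, power is about 91% for the t-test and 57% for signed-rank.

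**6. Other targets.** If the median is exactly 5 lb, signed-rank still rejects 12-47%, while the sign test holds its level (about 4.5%). Signed-rank is near level (5.2-5.6%) only for a null on the pseudo-median.

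**The case against.** **The data may not be skewed enough to matter.** A reader might infer that the plan's own figures force skew, so that the fallback becomes the real primary test: force cannot be negative, and a Normal with mean 5 and SD 5 puts 15.9% of patients below zero. The documents do not support this. The SD of 5 is stated beside a 5 lb difference, that is, a mean of 10 lb, where a Normal puts only 2.3% below zero. Nothing says the SD would stay at 5 if the mean were 5. This objection stands, so the results are given as a range starting at CV 0.2, where the excess is small.

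**The trigger is assumed.** No normality check is specified. If normality is meant of the sample mean, the switch would seldom occur at n = 130. This also stands: the two-stage rates are scenarios. It does not defend the rule, whose text concerns the data.

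**The choice makes no difference where the trial expects to be.** This is correct at a mean of 10 lb, and at SD 5 signed-rank still has 95-96% power at a mean of 7 lb. The direction of the error also works against the thesis of Section 2.0 that 5 lb is too restrictive, so a false claim that patients can lift more is not the main risk. But the plan covers several activities and takes 30% and 50% of the maximum, and nothing excludes means near 5 lb for some of these.

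**The target is not named.** If it were the median, the t-test would do worse than signed-rank (45% against 15% false positives at gamma skewness 1; 97% against 47% for the exponential). This is a fair reason to state the target first. It does not rescue the switch, which is off level for a mean or a median, and the plan never mentions a pseudo-median.

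**The plan names the rank sum test, not signed-rank.** That two-sample test does not fit one sample against a constant. Run literally against a column of 130 fives, it rejects 14% of the time with normal data, 52% at gamma skewness 1 and 95% for the exponential. Correcting the name alone would leave the present problem in place.

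**Conclusion.** The concern holds in conditional form. For a null on the mean, the planned switch gives up a test that stays near 0.05 at n = 130 for one that does not hold 0.05 when forces are right-skewed. The false-positive rate runs from about 6% (CV 0.2) to about 72% (lognormal, CV 1.0), given a true mean of 5 lb, the assumed shapes and the assumed trigger. It does not follow that any non-normality inflates the error, that the data will be skewed, or that the trial's main comparison is unsound at the effect it was sized for. The practical exposure is limited to activities, or 30% or 50% figures, whose mean lies near 5 lb. It should be corrected because the rule offers no benefit in return and the correction is cheap.

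**What to change.** In Section 1.2:

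1. State that the target is the mean force compared with 5 lb.
2. Make the one-sample t-test with its 95% CI the primary analysis whatever a normality check shows.
3. Add a bootstrap CI for the mean as a sensitivity analysis.
4. Delete the sentence that replaces the test when normality fails.
5. If forces are skewed, also report the median with a sign-test-based CI, labelled descriptive.

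If the investigators in fact want the median as the target, they should say so before analysis and pre-specify the sign test and its CI instead of the t-test. The cost is a short rewording of one section, with no extra patients, visits or data.

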1.0 OBJECTIVE

In a prospective study involving 130 cardiac rehabilitation patients muscular strength will be measured with a force dynamometer (PRIMUS) on six commonly performed activities. During the first session of cardiac rehabilitation, each subject's date of birth, height, and weight will be recorded. To ensure safety, cardiovascular nurse specialists and exercise physiologists will monitor the patients for hypertension (blood pressure $>240/110$ mm Hg), arrhythmias, angina, dizziness, pain, shortness of breath, and perceived exertion. The subjects will be asked to complete a pre-activity confidence survey. On the second day of cardiac rehabilitation, a clinical exercise specialist will use the PRIMUS equipment to obtain force measurements on the six activities including: rising from a bed, rising from a chair, opening a door, lifting an object from the floor and/or placing an object overhead. Following the performance of the activities, the patients will be asked to complete a post-activity confidence survey.

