3.0 PATIENT SELECTION

3.1 Patient Inclusion Criteria

All participants who are referred to Cardiac Rehabilitation with a qualifying diagnosis: CABG or VALVE. A total of 130 male and female volunteers who are 18 to 80 years of age will be asked to participate in the study. Subjects may be of any ethnic background and socio-economic status.

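### The fallback for the one-sample t-test against 5 lb is named as a two-sample test (Wilcoxon rank-sum), so it cannot be run as named; the normality sentence before it is also misworded (minor)

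*Combined protocol and SAP*

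**What the plan says.** Section 1.1 sets the question as whether the force measurements give "a different recommended weight lifted during the sternotomy healing process than the traditional gold standard of 5 pounds". The comparator is therefore a single fixed number.

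Sections 1.0 and 3.1 describe one group: "In a prospective study involving 130 cardiac rehabilitation patients muscular strength will be measured with a force dynamometer" and "A total of 130 male and female volunteers who are 18 to 80 years of age will be asked to participate in the study". No control arm or second sample appears in any section.

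Section 1.2 gives the main test: "We will use a one sample t-test to determine if a difference exists between the gold standard recommendation" and the force performed. It then states the assumption, "With this sample size, the data will likely be normally distributed, which is a necessary assumption to perform the one sample t-test", and the rule if the assumption fails: "we will proceed using a nonparametric alternative, the Wilcoxon Rank Sum Test". Earlier in the same section, continuous variables are to be summarised as "means and standard deviations or medians and interquartile ranges, if skewed".

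**The concern.** The Wilcoxon rank-sum test ranks two independent samples together and compares their rank sums. A single sample and a constant do not supply what it needs. The test is therefore not the nonparametric counterpart of a one-sample t-test, and the written rule for the main comparison under non-normality cannot be followed. An analyst who reaches that point must depart from the plan, after seeing the data, to run any test.

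The sentence that sets the trigger for the fallback has its own error. The number of patients does not alter the shape of the individual force values. It makes the sampling distribution of the mean close to normal, and that is what the t-test relies on at this size. Read literally, the plan would abandon the t-test for skewed data even where the t-test remains adequate.

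**Working it through.** **1. The plan's own figure.** Inputs from Section 1.2: n = 130, difference 5 lb, SD 5, two-sided alpha 0.05. Noncentrality = (5/5) × √130 = 11.40, df = 129. Power from the noncentral t distribution is above 99.9%, so the plan's claim of more than 90% is reproduced. The difference detectable with 90% power at n = 130 is about 1.43 lb.

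**2. Can the named fallback be run?**

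| Item | What the plan supplies | What the rank-sum test needs |
|---|---|---|
| Samples | one group of 130 (1.0, 3.1) | two independent groups |
| Comparator | constant, 5 lb (1.1) | a second set of observations |

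The only other comparison, confidence before and after the activities, is within patient, so the rank-sum test does not fit there either. A standard software call with one sample fails because the second sample is missing.

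**3. Does the likely intended test change the planning?** The one-sample signed-rank test on (value − 5), simulated with normal data at mean 10, SD 5 and n = 130, rejects in essentially 100% of runs, as does the t-test. Sample size and stated power stand.

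**4. Is correcting the name enough?** The fallback applies when data are not normal, so the relevant check uses skewed data. The documents give no force data; both shapes below are assumptions. In each, n = 130 and the true mean is exactly 5 lb. Figures are simulated two-sided rejection rates at 0.05, with runs agreeing to within about one percentage point.

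| Assumed shape | SD | t-test | Signed-rank |
|---|---|---|---|
| Gamma, shape 4, scale 1.25 | 2.5 | about 5% | about 16% |
| Lognormal, CV 1 | 5 | about 7% | about 72% |

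The signed-rank test is not malfunctioning here. It assumes symmetry and addresses the pseudo-median, the median of the average of two independent values. For the gamma shape, the sum of two values is gamma with shape 8, whose median in scale units is 7.67, so the pseudo-median is 7.67 × 1.25 / 2 = 4.79 lb, not 5. For the lognormal shape, the log-scale variance is ln(1 + 1²) = ln 2, so the median is 5 × exp(−ln 2 / 2) = 5/√2 = 3.54 lb, and the pseudo-median also lies below 5. If the lognormal is scaled so that its median is 5 lb, the signed-rank test still rejects in about 46% of samples, because it does not test the median of skewed data either.

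**5. Does n = 130 make the data normal?** For the lognormal shape, the Shapiro-Wilk test rejects normality in about 97% of samples at n = 30 and 100% at n = 130. The t-test at n = 130 nevertheless stays near its nominal size (about 7%), which supports a statement about the mean rather than about the data.

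**The case against.** The strongest reply is that this is a slip in a test name. Section 1.2 introduces the test as an alternative to a one-sample t-test, so a statistician would infer the one-sample Wilcoxon test at once. The fallback is conditional, and at the planned 5 lb difference either test would reject almost surely. The normality sentence, though loose, reaches the right practical message that the t-test is usable at this size. The provision for medians and interquartile ranges is generic to all continuous variables and is not evidence that skewed force data are expected. All of this stands, and it is why the point is minor. It does not make the written name correct: rank-sum and signed-rank are different tests, and no section resolves the matter.

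Three stronger readings are tempting, and the documents support none of them.

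- A reader might infer that the main comparison carries an inflated false-positive rate because the wrong test will be used. That would require inventing a second sample, for example repeated copies of 5, and the plan proposes nothing of the kind.
- A reader might infer that the sample size or power is undermined. Both rest on the t-test and are reproduced above.
- A reader might take the small power loss of the signed-rank test under normal data as the cost of the fallback. The fallback is meant for non-normal data, so that loss does not measure it.

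**Conclusion.** The fallback is wrong as written, and the error is minor. Section 1.2 names a two-independent-sample test for a one-sample comparison with a fixed 5 lb, so it cannot be run as named; the signed-rank test is the probable intention. The normality sentence is a secondary wording error that adds nothing to the severity.

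The naming error follows from the text alone and needs no assumption. The need to say which test decides rests on the skewed-data rates (about 16% and 72%, against about 5–7%). These depend on the assumed shapes and show the direction and possible range of disagreement; they do not predict what this study's data will do.

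**What to change.** In Section 1.2:

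1. Replace the name of the fallback with: *one-sample Wilcoxon signed-rank test of the differences from 5 lb*. Leave the tested variable as the plan defines it.
2. Reword the preceding sentence to: *With n = 130 the sample mean, rather than the data, will be approximately normal.*
3. Add a sentence that says which test decides, for example: *The t-test governs the conclusion about the mean; the signed-rank test, which assumes symmetry and addresses the pseudo-median, is reported as supportive if the data are not normal.*

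Step 3 turns the fallback from a replacement into a supportive analysis, so the sponsor should adopt it knowingly. Reporting both tests without such a rule would leave two answers to two different questions and no stated way to choose.

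The cost is two rewordings, one added sentence, and one extra reported analysis if the data are not normal. That analysis may disagree with the t-test when data are skewed, because its target differs. Sample size, data collection and patient burden do not change.

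### The secondary confidence endpoint has three overlapping readings, no main one, and no paired analysis of the ordered 7-point change

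*Combined protocol and SAP*

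**What the plan says.** Section 1.1 gives the endpoint its role: "A secondary endpoint data obtained will be scores from the pre and post-activity questionnaires".

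Section 1.2 describes the measurement. On timing, "2 surveys will be administered: 1 prior to treatment and 1 after treatment"; on the scale, "subjects will be asked to rate their confidence using a 7-point Likert scale to perform selected daily tasks". The same patients answer both times, so the data are paired and ordinal. The number of tasks rated is not given.

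On analysis, Section 1.2 says that "perceptions of confidence will be reported and analyzed in several ways. We will consider the changes from each of the 7 categories". That is the first of three readings. The second is a top-box percentage before and after, and the third regroups the answers as positive, neutral or negative.

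For confidence, the section names no main reading, test, effect measure, interval, significance level, cut-points for the three strata, or rule for several tasks. The t-test, its nonparametric fallback and the 0.05 level all belong to the force comparison.

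**The concern.** The readings are not separate questions. Top box, taken as the highest category, is one of the seven categories and also lies inside the positive stratum. With no main reading named, the one that looks best can become the result once the data are seen.

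None of the three is stated to be each patient's own movement along the scale. Comparing categories one at a time ignores their order. Top box reduces seven levels to two, and the strata reduce them to three. If changes are also computed as differences between two sets of percentages, the within-patient correlation goes unused. That costs precision in a study that has already collected paired data.

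The endpoint carries some weight despite being secondary: the risk/benefit paragraph of Section 6.0 relies on patients gaining confidence.

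**Working it through.** **The plan's own figure.** The only power statement concerns force: 130 subjects, difference 5 lb, SD 5, two-sided 0.05. The normal approximation is Φ(δ√n/SD − 1.96) = Φ(5 × 11.40/5 − 1.96) = Φ(9.44), above 99.9%. This agrees with the stated power of over 90%, but it says nothing about confidence, for which no figure is given.

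**Inputs for confidence.** From Section 1.2: n = 130, a 7-point item, before and after in the same subjects. Assumed, because the documents give none: a latent normal response with pre/post correlation 0.3 to 0.7; baseline about 27% top box and 73% positive; strata 1–3, 4 and 5–7; a latent shift of 0.2 SD; one task. All figures are per task.

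**Power at a 0.2 SD shift** (2,000 simulated trials per setting):

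| Analysis | Corr. 0.3 | Corr. 0.5 | Corr. 0.7 |
|---|---|---|---|
| Signed-rank on 7-point change | 42% | 51% | 71% |
| Top box, paired (McNemar) | 27% | 30% | 40% |
| Top box, unpaired proportions | 22% | 17% | 17% |

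Allowing for repeat simulations and the form of McNemar test, the ranges are about 40% to 72%, 22% to 40% and 15% to 22%. At a 0.25 SD shift and correlation 0.6 the order is the same: about 79%, 40% to 45%, and 28% to 30%.

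**Chance of at least one positive with no true change.** This supposes that each reading is tested at 0.05.

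- Signed-rank alone: 4.2% to 5.6%.
- Best of three (signed-rank standing in for the full-scale reading, top box, positive): 10% to 13%, or from about 7% across repeat simulations. Three independent tests would give 1 − 0.95³ = 14.3%.
- Every category and stratum as its own paired contrast: 18% to 21%, up to about 24% across simulations. This figure depends on how sparse categories are tested; an exact McNemar test keeps it down. Top box is category 7 and, with these cut-points, neutral is category 4, so seven categories and three strata make nine distinct contrasts. Independence would give 1 − 0.95⁹ = 37.0%.

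Ignoring pairing does not itself create false positives. The unpaired top-box test rejected in only 0.6% to 2.8% of null trials. Its cost is power.

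**Interval width for top box.** Assume 30% before and 45% after. With r the correlation between the two binary responses:

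- Unpaired SE = √[(0.30 × 0.70 + 0.45 × 0.55)/130] = √(0.4575/130) = 0.0593.
- Paired SE = √[(0.4575 − 2r√(0.21 × 0.2475))/130] = √[(0.4575 − 0.4560r)/130].

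| Latent corr. | r | Paired SE | Unpaired/paired |
|---|---|---|---|
| 0.3 | 0.185 | √(0.3731/130) = 0.0536 | 1.11 |
| 0.6 | 0.389 | √(0.2801/130) = 0.0464 | 1.28 |

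Dropping the pairing widens the interval by about 11% to 28% over this range.

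**The case against.** The strongest reply is that this is a secondary endpoint in a single-group study, with no power claim and no planned test. All three readings are listed in advance, so reporting all of them would limit selection. This stands in part: it is why the error rates above are conditional, and why the point is a recommendation rather than a fatal flaw. It does not remove the gap, because the plan says confidence will be analysed and does not label any reading descriptive.

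Several stronger readings are tempting, but the documents do not support them.

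- *The plan discards the pairing.* It is silent. Changes from a category could mean within-patient movement. Only top box is explicitly a percentage, although Section 1.2 reports categorical variables generally as frequencies and percents.
- *All readings are collapsed.* The first keeps all seven categories; only top box and the strata collapse the scale.
- *Section 1.2 contradicts Section 1.1.* It describes ways to summarise the ratings. What is missing is an analysis of the score itself.
- *The force fallback shows that confidence will be mis-tested.* The sentence "we will proceed using a nonparametric alternative, the Wilcoxon Rank Sum Test" concerns force only and is not evidence about confidence.
- *Three readings give a 20% false-positive rate.* That size appears only when every category and stratum is tested separately.
- *Ignoring pairing widens the interval by 41%.* That needs r = 0.5 between the binary responses (0.0593/0.0420 = 1.41), which corresponds to a latent correlation near 0.75.

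It is also fair that signed-rank is not the only defensible choice; a composite score or an ordinal mixed model would serve. What matters is that one paired, ordered analysis is named beforehand.

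**Conclusion.** The concern holds in this form: three overlapping readings, no main one, no paired method specified, and no analysis of the ordered 7-point change. Pairing and order may be lost, and the choice of result is left open. In the assumed settings, moving from signed-rank on the score to unpaired top box takes power at a 0.2 SD shift from about 40%–72% to 15%–22%. The error rates of about 7% to 13% (three readings) and 18% to 24% (every contrast) apply only if the readings are tested at 0.05. Correlation, baseline, cut-points and shift are all assumptions, so the figures show direction and rough size. Several tasks would add further comparisons. The change should be made, but it does not affect the primary force comparison.

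**What to change.** In Section 1.2, name as the main confidence analysis each patient's post-minus-pre 7-point score for each task, tested with the Wilcoxon signed-rank test and reported with a 95% CI for the change. State how unchanged scores are handled, list the tasks, and apply Holm adjustment across tasks if claims are made per task. Keep the category, top-box and positive/neutral/negative summaries as descriptive support, with cut-points defined. If they are tested, use paired methods: McNemar for top box and Stuart-Maxwell for the strata.

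The cost is a few sentences and no new data. The downside is that top-box and category changes can no longer be headline results.
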